6.2. Study Process

6.2.1. Study Process

6.2.1.1. Enrollment

The investigator will screen the subjects according to the inclusion and exclusion criteria after obtaining the ICF signed by the subjects (or their guardians). After the subjects pass the screening, at the end of cerebral DSA angiography and before using the revascularization device, the investigator will randomize the subjects into the test group and the control group in the randomization order, and the enrollment will be considered successful.

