- 8) Randomization: An electronic randomization system is logged into for randomization.

* If any of the micro-guidewire and microcatheter does not pass through the thrombus segment of the target vessel during the operation, or if the thrombectomy device is not used for thrombectomy, this subject is statistically processed as having a blank randomization number;

6.2.2. Device Specifications (recommend the operation method, and the operator may make slight modification according to the actual situations)

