6.2.2.1. Preparations

1. Administer anticoagulant and antiplatelet drugs according to standard guidelines.
2. With the aid of angiography, determine the location and size of the area for recanalization.
3. Select a revascularization device based on the product specification/model.
4. To achieve optimal use of the revascularization device and reduce the risk of thromboembolic complications, maintain continuous flushing of the following lumens:
 - a) Between femoral sheath and guiding catheter;
 - b) Between guiding catheter and microcatheter;
 - c) Between microcatheter and push rod/revascularization device.

Check all connections to ensure that no air enters the guiding catheter or microcatheter during continuous flushing.

5. Deliver the appropriate guiding catheter as close as possible to the thrombus site by standard methods. If required in subsequent steps, the size of the

guiding catheter should be appropriate for thrombus recovery. Connect the RHV to the guiding catheter and then connect an infusion line for continuous flushing.

6. Based on the product specification/model, select the microcatheter suitable for delivering the revascularization device.
7. Attach a second RHV to the microcatheter and then connect an infusion line for continuous flushing.
8. Set the flushing speed according to standard guidelines.
9. Deliver the microcatheter over the appropriate guidewire until the end of the microcatheter is distal to the thrombus so that the effective length portion of the revascularization device covers each side of the thrombus in the vessel when fully deployed. Tighten the RHV around the microcatheter.

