8.6. Selection Criteria for Subjects Included in the Analysis and

Justification

Statistical analysis will be carried out on the basis of the following analysis populations. The analysis populations will be clearly defined before the start of statistical analysis. And the analysis populations in this study include:

Full Analysis Set (FAS): The set of subjects determined following the intent-to-treat (ITT) principle refers to the data set constituted by all subjects who participate in the randomized study and receive the investigational product. For patients in whom the primary effectiveness endpoint is not observed, missing data are proposed to be carried forward using the WOCF (Worst Observation Carry Forward).

Per-Protocol Set (PPS): refers to the subgroups of treatment population where the study has been completed with the major protocol violations excluded (which means that the subjects violate the inclusion criteria or exclusion criteria, etc.).

Safety Set (SS): refers to the set of all subjects who receive the investigational device and complete safety evaluation at least once.

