1.4. Trial Process

Visit time Visit contents	Screening/Baseline period	Treatment period	Observation period	Follow-up period	
	Preoperatively -1 d ~ 0 d	Day of operation/0 d	Postoperatively 24 h ± 12 h	Postoperatively 7 d ± 2 d	Postoperatively 90 d ± 14 d
Signing of ICF	×				
Medical history	×				
Preoperative diagnosis	×				
Vital signs ¹	×		×	×	
NIHSS score ²	×		×	×	
mRS score ³	×				×
Laboratory test ¹	×		×		
Pregnancy test ⁵	×				
Cerebral CT or MR ^{6,7}	×		×		
Cerebrovascular DSA ⁷	×				
Verification of eligibility criteria		×			
Randomization		×			
Operations		×			
Antiplatelet and anticoagulant medication	×	×	×	×	×
Adverse event		×	×	×	×
Device defect		×			

Figure1 Study Flowchart

Note:

- 1) Vital signs include heart rate and blood pressure.
- 2) NIHSS score: assessing the degree of neurological impairment of the subject.
- 3) MRS score: assessing the degree of disability of the subject.
- 4) Laboratory tests (The laboratory test results at 24 h preoperatively are accepted during the screening period, and one laboratory test within 9d postoperatively is sufficient):
- 5) Blood routine: Red blood cell, hemoglobin, white blood cell count, and platelet count
- 6) Blood chemistry: Urea nitrogen (urea), serum creatinine, blood glucose
- 7) Coagulation: Prothrombin time, activated partial thromboplastin time and INR
- 8) Only for women of childbearing potential who are planning to become pregnant, blood or urine pregnancy test

result is acceptable.

- 9) Cerebral CT or MR is performed when the onset time is ≤ 6 h; cerebral CT or MR is performed when the onset time is 6 (exclusive)-24h (inclusive) to determine whether ASPECTS score ≥ 6 is met; (if immediate CT perfusion imaging or MR perfusion imaging is feasible, CTP or MRP is recommended to assist in the assessment of the infarct core to determine whether ASPECTS score ≥ 6 is met).
 - 10) CT or MRI images and DSA images during thrombectomy are burned on a CD in DICOM format and evaluated by a central interpretation room.
 - 11) Randomization: An electronic randomization system is logged into for randomization.
- * If any of the micro-guidewire and microcatheter does not pass through the thrombus segment of the target vessel during the operation, or if the thrombectomy device is not used for thrombectomy, this subject is statistically processed as having a blank randomization number.

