2.2. Safety Endpoints

1. Incidence of symptomatic intracranial hemorrhage within 24 hours postoperatively: Symptomatic intracranial hemorrhage refers to intracranial hemorrhage (cerebral parenchymal hematoma, subarachnoid hemorrhage, subdural hematoma, ventricular hemorrhage) accompanied by neurological deterioration (NIHSS score increase ≥ 4 points compared to preoperative). Incidence of symptomatic intracranial hemorrhage within 24 hours = Number of subjects in this group with symptomatic intracranial hemorrhage confirmed by CT or MR within 24 hours / Number of subjects in this group undergoing intracranial thrombectomy with a thrombectomy stent $\times 100\%$. CT or MR findings were evaluated by the central reading center.
2. All-cause mortality within 90 days postoperatively: All-cause mortality rate = Number of deaths in this group / Total number of subjects in this group undergoing intracranial thrombectomy with a thrombectomy stent $\times 100\%$.
3. Incidence of SAEs, incidence of AEs.
4. Device defects rate.

3. Analysis Set

Full Analysis Set (FAS): A population defined according to the intention-to-treat principle, comprising all subjects who participated in randomization and received the study product. For patients in whom the primary efficacy endpoint was not observed, missing data will be carried forward using

the Worst Observation Carry Forward (WOCF) strategy.

Protocol-Compliant Set (PPS): Refers to the subgroup of the treated population that completed the trial, excluding those with major protocol deviations (e.g., subjects violating inclusion or exclusion criteria).

Safety Set (SS): Refers to the population of all subjects who used the study device and had at least one safety assessment.

Efficacy analyses will be conducted on the basis of the full analysis set and the per-protocol set. Additionally, all baseline demographic analyses will be performed on the full analysis set, while safety evaluations will be conducted on the safety set.

4. Missing Data Imputation

For patients in the FAS who did not have an observed primary efficacy endpoint, worst-case imputation was applied, defined as failure to achieve immediate reperfusion in the target vessel. No imputation was performed for secondary endpoints or efficacy data in the PPS. Missing safety data were not imputed.

5. Statistical Analysis Methods

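### Randomised subjects without crossing or device use are dropped as blank numbers, so the FAS is not intention-to-treat and can favour non-inferiority if the test arm has more of them

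*Protocol*

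**What the plan says.** **The rule.** The note under the flowchart in Protocol 6.2.1.3 has two triggers. The first is failure to cross: "If any of the micro-guidewire and microcatheter does not pass through the thrombus segment of the target vessel during the operation". The second is non-use: "if the thrombectomy device is not used for thrombectomy, this subject is statistically processed as having a blank randomization number". SAP 1.4 repeats the note with the same consequence: "this subject is statistically processed as having a blank randomization number".

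**Timing.** Protocol 6.2.1.1 places randomisation after angiography and before crossing: "at the end of cerebral DSA angiography and before using the revascularization device, the investigator will randomize the subjects". Under Protocol 6.2.1.2 the investigator receives the allocation from the system and picks the matching product. Protocol 6.1.2 blinds only the central image reading.

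**Analysis sets.** Protocol 8.6 says the FAS follows the intent-to-treat principle, yet it is "constituted by all subjects who participate in the randomized study and receive the investigational product". SAP section 3 agrees: "comprising all subjects who participated in randomization and received the study product". The PPS is a subgroup of the treated population, and the safety set requires use of the device.

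**Denominator and imputation.** The primary success rate in Protocol 6.1.6 and SAP 2.1.1 divides by subjects treated with the device. Worst-case imputation in SAP section 4 applies to FAS members whose primary endpoint was not observed.

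**The concern.** Whether a subject becomes a blank number is settled after allocation, during an open-label procedure, by someone who knows the arm. Part of the route to that outcome is tied to the device. Protocol 6.2.2.1 says: "Based on the product specification/model, select the microcatheter suitable for delivering the revascularization device". Protocol 6.1.4.1 lists minimum microcatheter inner diameters of 0.017, 0.021 and 0.027 inch across the test models. Crossing, and the decision not to use the assigned device, could therefore differ between arms.

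If they do, the treated subjects in the two arms are no longer the groups that randomisation created. Nothing else in the plan makes up for this. The FAS, PPS and safety set omit the same subjects, and imputation never reaches them. No all-randomised sensitivity analysis is planned, and no table lists blank numbers by reason. The pass/fail rule in Protocol 8.2 rests on this comparison.

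The term *used for thrombectomy* is also undefined. Protocol 6.2.2.2 tells the operator to stop if the stent meets excessive resistance. Whether a subject with a device inserted but never deployed counts as used or blank is left open.

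**Working it through.** **The plan's own figure.** Inputs from Protocol 7.2.1: 89% in both arms, margin 12.5 points, one-sided alpha 0.025, power 80%, dropout 10%.

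n = (1.960 + 0.842)² × (2 × 0.89 × 0.11) / 0.125² = 7.849 × 0.1958 / 0.015625 = 98.4, so 99 per arm. Then 99 / 0.90 = 110. Both figures reproduce. Power is 80.3% at 99 and 84.2% at 110 per arm.

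**Chance of wrongly declaring non-inferiority.** The documents give no blank rates, so these are assumptions: 110 randomised per arm, 2% blanks in control, 89% success among treated controls, and blanks not recanalised. The true all-randomised difference is set at exactly -12.5 points.

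- All-randomised control rate: 0.89 × 0.98 = 0.872.
- All-randomised test rate: 0.872 - 0.125 = 0.747.
- Treated test rate with blank share b: 0.747 / (1 - b).
- Analysed numbers: 110 × 0.98 = 107.8 in control and 110 × (1 - b) in test.
- P(declare) = Φ((d + 0.125)/SE - 1.96), where d is the treated difference and SE = √[p_T(1-p_T)/n_T + p_C(1-p_C)/n_C].

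| Test blanks | n_T | Treated test rate | d (points) | SE | P(declare) |
|---|---|---|---|---|---|
| 0% | 110 | 0.747 | -14.3 | 0.0512 | 0.011 |
| 2% | 107.8 | 0.762 | -12.8 | 0.0509 | 0.022 |
| 3% | 106.7 | 0.770 | -12.0 | 0.0507 | 0.032 |
| 5% | 104.5 | 0.787 | -10.3 | 0.0501 | 0.063 |
| 7% | 102.3 | 0.803 | -8.7 | 0.0495 | 0.118 |

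For the 5% row: (-0.1035 + 0.125)/0.0501 - 1.96 = -1.53, and Φ(-1.53) = 0.063. With 5% blanks in each arm the figure is 0.018. Error rises above 0.025 only when the test arm has more blanks than control.

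The normal approximation is slightly low. In a neighbouring scenario (89% among all randomised controls, blanks 5% test and 2% control) it gives 0.067, against 0.075 by simulation.

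**One possible trial.** Control 98/110; 110 randomised to test with 5 blanks and 93 successes; Wald limits.

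- Blanks excluded: 93/105 - 98/110 = -0.5 points. Lower limit -0.0052 - 1.96 × 0.0430 = -8.9%, which passes.
- Blanks kept as failures: 93/110 - 98/110 = -4.5 points. Lower limit -0.0455 - 1.96 × 0.0455 = -13.5%, which fails.

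With 4 test blanks and 94 successes, keeping them as failures gives -12.4% and still passes.

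**Power when the arms are truly equal (89% among treated, 110 randomised per arm).**

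| Blanks in each arm | Excluded, as planned | All kept as failures |
|---|---|---|
| 0% | 84% | 84% |
| 2% | 83% | 79% (p = 0.872) |
| 5% | 82% | 73% (p = 0.8455) |

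**The case against.** The strongest reply is that the direction of any bias is not shown.

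- A reader might infer that the rule necessarily favours the test device. The documents do not support that. Equal blanks do not inflate the error, and more blanks in control work against the test device.
- A reader might also infer that blank subjects are device failures. They are a mixed group. Crossing precedes stent insertion, the rule also covers the guidewire (which is not matched to the device), and failure may be anatomical. Access too tortuous for the device is already an exclusion criterion. Protocol 6.1.4 gives no microcatheter size for the control device, so arm dependence is plausible but not demonstrated.
- The subjects are not erased. Entries in the randomisation system cannot be deleted (Protocol 6.2.1.2), numbers are not reused (Protocol 6.1.5.3), and SAP Table 3 appears to set randomised and FAS counts side by side by arm. The size of a shortfall should be visible, though not its reasons.
- Protocol 8.1 allows 10% for any exclusion from the primary analysis. That protects precision, not comparability, and its examples do not mention blank numbers.
- Scoring every blank subject as a failure is not what SAP section 4 says. That rule covers an unobserved endpoint, whereas a blank subject may have an observed final mTICI after other treatment.

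These points limit the claim about direction and shape the fix. They do not remove the exclusion after randomisation, and the plan neither prevents an imbalance nor explains one.

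**Conclusion.** The point holds in conditional form. Both documents exclude randomised subjects on events after open-label allocation, and every planned analysis set omits them. The FAS is not an intention-to-treat set, whatever its label.

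The primary comparison can be biased toward non-inferiority if blanks are more frequent in the test arm. On the stated assumptions the nominal 0.025 becomes about 0.063 with 5% test blanks against 2% in control, and about 0.118 with 7% against 2%. It stays below 0.025 when the shares are equal or control has more. In the example trial, five test-arm blanks and none in control reverse the conclusion.

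The exclusion itself is certain from the text. The blank shares are assumptions, and the calculation counts each blank as not recanalised; if some are recanalised by other means, the effect is smaller. The Wald limits are indicative, because SAP Table 24 names an exact interval. The change should still be made before database lock, because the pass/fail decision depends on this analysis and nothing else in the plan covers the gap.

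**What to change.** 1. Delete the blank-number rule from Protocol 6.2.1.3 and SAP 1.4. Define the FAS as all randomised subjects in their assigned arm, and align the primary denominator in Protocol 6.1.6 and SAP 2.1.1.
2. For subjects with no crossing or no device use, take the centrally read final mTICI where observed and count failure where it is missing.
3. Add a sensitivity analysis that counts all such subjects as failures. Present it as a stress test and not as the existing imputation rule.
4. Keep the treated-only set as supportive, and require the all-randomised analysis to meet -12.5% before non-inferiority is claimed.
5. Define *used for thrombectomy*, including a device inserted but not deployed.
6. Tabulate these subjects by arm and reason, and report their adverse events.

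**Cost.** The change is to wording in both documents and a few table lines; the subjects are already in the randomisation system. Observed rates and power become somewhat less favourable. If every blank counted as a failure, power at 110 per arm would be about 79% with 2% blanks in each arm and 73% with 5%, against 83% and 82% with blanks excluded. That loss is a price of the fix and not damage done by the present rule.

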6.2.2.1. Preparations

1. Administer anticoagulant and antiplatelet drugs according to standard guidelines.
2. With the aid of angiography, determine the location and size of the area for recanalization.
3. Select a revascularization device based on the product specification/model.
4. To achieve optimal use of the revascularization device and reduce the risk of thromboembolic complications, maintain continuous flushing of the following lumens:
 - a) Between femoral sheath and guiding catheter;
 - b) Between guiding catheter and microcatheter;
 - c) Between microcatheter and push rod/revascularization device.

Check all connections to ensure that no air enters the guiding catheter or microcatheter during continuous flushing.

5. Deliver the appropriate guiding catheter as close as possible to the thrombus site by standard methods. If required in subsequent steps, the size of the

guiding catheter should be appropriate for thrombus recovery. Connect the RHV to the guiding catheter and then connect an infusion line for continuous flushing.

6. Based on the product specification/model, select the microcatheter suitable for delivering the revascularization device.
7. Attach a second RHV to the microcatheter and then connect an infusion line for continuous flushing.
8. Set the flushing speed according to standard guidelines.
9. Deliver the microcatheter over the appropriate guidewire until the end of the microcatheter is distal to the thrombus so that the effective length portion of the revascularization device covers each side of the thrombus in the vessel when fully deployed. Tighten the RHV around the microcatheter.

6.2.2.2. Delivering Revascularization Device

10. Insert the distal portion of the introducer sheath into the RHV connected to the microcatheter. Tighten the RHV and verify that fluid exits the proximal end of the introducer sheath.
11. Loosen the RHV and push the introducer sheath until its distal end is securely seated in the microcatheter hub. Tighten the RHV around the introducer sheath to prevent blood backflow, but the damage may occur to the device if tightened too tightly as the stent is pushed into the microcatheter. Verify that there are no air bubbles in the system.
12. Push the push rod in a smooth continuous manner so that the thrombectomy stent is delivered into the microcatheter. Once the flexible portion of the push rod enters the microcatheter, loosen the RHV and remove the introducer sheath from the proximal end of the push rod. Upon completion, tighten the RHV around the push rod. Continued tight attachment of the introducer sheath to the inner lumen of the microcatheter will block normal flushing of the RHV and lead to backflow of blood into the microcatheter.
13. After visually confirming that the flushing fluid input is normal, loosen the RHV and push the push rod.
14. Once the proximal marker of the revascularization device enters the microcatheter, start the X-ray imaging system. With the aid of the x-ray imaging system, carefully deliver the stent until its distal marker is aligned with the distal microcatheter, and the stent remains in such a position that, when the device is completely deployed, its effective length portion covers each side of the thrombus in the vessel.
 - ✧ Warning: If excessive resistance encounters in the advancement of the stent, stop and identify the cause. Advancing the thrombectomy stent

against heavy resistance may damage the device and/or injure the patient.

6.2.2.3. Deploying Revascularization Device

15. Loosen the RHV around the microcatheter. Fix the push rod so as to maintain the position of the thrombectomy device while carefully withdrawing the microcatheter to the proximal end.
16. Withdraw the microcatheter until it approaches the proximal marker of the revascularization device. Tighten the RHV to prevent movement of the push rod. The effective length of the revascularization device should be greater than each side of the thrombus.
17. Tighten the RHV around the microcatheter. Angiographically assess the target vessel for flow patency.
18. Ancillary medical techniques (i.e. thrombolytics, etc.) may be used according to standard guidelines.

6.2.2.4. Withdrawing the Device

19. If using a balloon guiding catheter, inflate the balloon as directed on the balloon catheter label to occlude the vessel.
20. Ensure that the proximal marker of the stent is inside the microcatheter and loosen the RHV around the microcatheter so that it moves but remains sealed.
21. Slowly withdraw the microcatheter and the revascularization device as a whole to the end of the guiding catheter while aspirating the guiding catheter with a 60 cc syringe. Do not advance the stent deployed to the distal end.

Caution: Ensure that the proximal marker of the revascularization device remains within the microcatheter.

22. Perform vigorous aspiration of the guiding catheter with a syringe, while withdrawing the revascularization device and microcatheter into the guiding catheter. Continue aspiration of the guiding catheter until the thrombectomy stent and microcatheter are almost withdrawn from the guiding catheter.

Note: If it is difficult to withdraw the guiding catheter, first deflate the balloon (if the balloon guiding catheter is used), and then withdraw the guiding catheter, microcatheter and revascularization device to the arterial sheath while maintaining aspiration, and withdraw together with the arterial sheath if necessary.

✧ Warning: If excessive resistance encounters in the withdrawal of the revascularization device, discontinue thrombectomy and identify the cause.

23. Open the RHV of the guiding catheter, and allow the microcatheter and revascularization device to be smoothly withdrawn. Take care of device

interference and prevent air from entering the system.

24. Continue aspiration of the guiding catheter and ensure there is no thrombus material in the guiding catheter.
25. Deflate the balloon if the balloon guide catheter is used.
26. If an additional attempt to restore flow is required, take the following steps:
 - a) Use a new revascularization device, and then:
 - i. Repeat the above steps from the "Preparations" section.
 - b) Use the same revascularization device, and then:
 - i. Clean the device with normal saline.

Caution: Do not use other solvents or autoclaves.
 - ii. Inspect the device for damage carefully.
 - iii. In case of any damage, use a new device and follow the steps described above (starting with the "Preparations" section) for subsequent flow restoration attempt.
 - iv. Use of a damaged device may result in further damage to the device and/or patient injury.

